9.3. Population of Interest

The analyses will be based on the ITT and Efficacy PD population, unless otherwise specified.

9.4. Strategy for Intercurrent (Post-Randomization) Events

Any intercurrent events are taken to be irrelevant for the endpoints and the endpoints will be summarized based on available and observed data.

Analysis of change from baseline in the respective QoL parameter at each assessment visit will follow the strategy below.

Intercurrent events	Strategy
Study withdrawal / Intermittent missing	The following hypothetical scenario is considered to assess what would have happened if the event did not occur. Analysis using MMRM assume missing at random mechanism, that is the observations of missing depend on just observed values, not on unobserved values.

9.5. Statistical Analyses / Methods

Details of the planned displays are provided in [Appendix 10: List of Data Displays](#) and will be based on GSK data standards and statistical principles.

Unless otherwise specified, endpoints / variables defined in Section 9.1 will be summarized using descriptive statistics and listed.

9.5.1. Statistical Methodology Specification

Endpoint / Variables

 Change from baseline in the respective QoL parameter at each assessment visit
Model Specification

 Analyses will be repeated for each QoL parameter (SF-36 HR-QoL scores/EQ-5D-5L index value/EQ-VAS score) using MMRM as specified in Section 7.3.5.1: Note that the QoL parameters are no need to be log-transformed as opposed to some of the iron parameters.
Model Results Presentation

 The adjusted mean change from baseline will be presented with the associated 95% CIs by treatment at each assessment visit. The adjusted treatment difference (daprodustat – epoetin beta pegol) for change from baseline will also be presented with the associated 95% CI at each assessment visit.
Subgroup Analyses

 Similar to the respective QoL parameters, the above analysis will be repeated by prior ESA use subgroup (See Section 5.4.2) in the same manner. The subgroup analyses will be based on the ITT and Efficacy PD population. If there is a problem with convergence for a subgroup, the result of the subgroup will not be displayed.

10. PHARMACOKINETIC ANALYSES

10.1. Pharmacokinetic Analyses

10.1.1. Endpoint / Variables

The details of the planned displays are presented in [Appendix 10: List of Data Displays](#).

Endpoints	Untransformed				Log-Transformed			
	Summary		Individual		Summary		Individual	
	F	T	F	L	F	T	F	L
Plasma Concentrations of Daprodustat	Y ^{[1][2]}	Y	Y ^[1]	Y				
Derived PK Parameters	Y ^[3]	Y ^[3]	Y ^[3]	Y		Y ^[3]		
Dose Normalized PK Parameters	Y ^[3]	Y ^[3]	Y ^[3]	Y		Y ^[3]		

NOTES :

- T = Table, F = Figures, L = Listings, Y = Yes display generated.
 - Summary = Represents TFL related to any summaries (descriptive statistics) of the observed raw data.
 - Individual = Represents FL related to any displays of individual subject observed raw data.
1. Linear and Semi-Log plots will be created on the same display.
 2. Separate Mean (\pm SD) and Median plots will be generated.
 3. Individual PK parameters calculated based on less than 4-time point concentrations, or any time deviated concentration, or concentrations obtained in the less interval of last two treatment administrations than 12 hours will be omitted from summaries and figures.

10.1.1.1. Drug Concentration Measures

Refer to [Appendix 5: Data Display Standards & Handling Conventions \(Section 15.5.3 Reporting Standards for Pharmacokinetic\)](#)

Concentrations of daprodustat in plasma will be listed and summarized by dose group and nominal time. Individual plasma concentration-time profiles and median/mean profiles by dose group will be plotted. Each of figures will contain one plot on the untransformed scale (i.e. a linear plot) and one plot on the log transformed scale (i.e. a log-linear plot).

10.1.1.2. Derived Pharmacokinetic Parameters

Derivation of pharmacokinetic parameters will be performed by, or under the direct auspices of, Clinical Pharmacology Office, GlaxoSmithKline K.K.

Pharmacokinetic parameters will be calculated by standard non-compartmental analysis according to current working practices and using the currently supported version of WinNonlin (version 6.3 or higher). All calculations of non-compartmental parameters will be based on actual sampling times. Pharmacokinetic parameters listed will be determined from the plasma daprodustat concentration-time data, as data permits.

Parameter	Parameter Description
AUC(0-4)	Area under the concentration-time curve from time zero to the time of the last quantifiable concentration (C(last)) will be calculated using the linear trapezoidal rule for each incremental trapezoid and the linear trapezoidal for each decremental trapezoid. The concentration at 0 hr will be set to 0.
Cmax	Maximum observed concentration, determined directly from the concentration-time data.
Tmax	Time to first occurrence of Cmax will be obtained directly from the concentration-time data.

NOTES:

- Additional parameters may be included as required.
- C(last) is expected to be the concentration observed at 4 hours after the most recent dose.

10.1.2. Summary Measure

Refer to Section [15.5.3](#) for the display standards.

- ***Plasma Daprodustat Concentrations***

Non-transformed and log-transformed plasma concentration at every scheduled time point will be summarized at Week 12, Week 24, and all visits (i.e., pooled analysis of Week 12 and Week 24) by dose level. Non-transformed plasma concentration of daprodustat will be summarized using mean, 95% CI, standard deviation, median, minimum, and maximum. Log-transformed plasma concentration of daprodustat will be summarized using geometric mean, 95% CI of geometric mean, standard deviation of log-transformed data and between subject coefficient of variation (%CVb).

- ***PK Parameters***

Non-transformed and log-transformed PK parameters will be summarized at Week 12, Week 24, and all visits (i.e., pooled analysis of Week 12 and Week 24) by dose level. Non-transformed PK parameters of daprodustat (AUC(0-4), Cmax, and Tmax) will be summarized using mean, 95% CI, standard deviation, median, minimum, and maximum. Log-transformed PK parameters of daprodustat (AUC(0-4), Cmax, Tmax) will be summarized using geometric mean, 95% CI of geometric mean, standard deviation of log-transformed data and between subject coefficient of variation (%CVb).

Dose normalized PK parameters (non-transformed and log-transformed) will also be summarized as the same by dose level. In summary of dose normalized PK parameters, summary tables by tablet strength (non-transformed and log-transformed) will be provided.

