modified ITT (mITT)	
 Consist of all ITT subjects who have at least one Hgb measurement during the efficacy evaluation period. Subjects will be analyzed according to randomized treatment. This population will be the primary population for an assessment of superiority. 	
 Study Population Efficacy
Per-Protocol (PP)	
 Consists of all mITT subjects who are not major protocol violators. This population will be used for efficacy sensitivity analyses. Protocol deviations that would exclude subjects from the PP population are defined in Section 4.1(Protocol Deviations) and Appendix 1: Protocol Deviation Management and Definitions for Per Protocol Population. 	
 Efficacy
Pharmacokinetic (PK)	
 Consists of all GSK1278863-treated subjects from whom PK samples are collected and analyzed. 	
 PK

NOTES :

- Basically, enrolled population will be the same as randomized population because a subject is going to be given randomized number as soon as passed screening.
- Refer to [Appendix 10](#): List of Data Displays which details the population used for each display.
- Refer to [15.6.2](#) for handling rescreened subjects.

[1]: Only subjects receiving incorrect randomized treatment for the duration of their study participation will be analyzed according to the treatment received. Otherwise, subjects will be analyzed according to the treatment to which they were randomized.

Figure 1 Analysis Populations

NOTES :

- [1]: Subjects who never passed screening even if rescreened
- [2]: Subjects who are not given randomization number
- [3]: Subjects who never receive study treatment
- [4]: Subjects who do not have Hgb measurement at both baseline and at least one scheduled visits following the baseline
- [5]: ESA non-users in Cohort 1 subjects
- [6]: Subjects who have no Hgb measurement during the efficacy evaluation period
- [7]: Subjects who are major protocol violators (See Section 4.1 and [Appendix 1](#))

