5.4.2. Examination of Subgroups

The list of subgroups may be used in descriptive summaries and statistical analyses.

Subgroup	Categories
Prior ESA Use ^[1]	Non-user, User
Baseline Hgb (g/dL) ^{[1][2]}	ESA non-users: <=9.5, >9.5 ESA users: <11.0, >=11.0
Age (year)	< 65, >=65
Sex	Female, Male
Prior ESA Dose (IU/week)	<4,500, >=4,500 ^{[3][4]}
Prior ESA Type	Epoetin, Epoetin beta pegol, Darbepoetin alfa
ERI ^[3]	< median, >= median
Baseline Iron Use ^[5]	Yes, No

Subgroup	Categories
Baseline Weight (kg)	< 55, >=55
Baseline BMI (kg/m ²)	<20, >=20
History of Diabetes ^[6]	Yes, No
Dialysis ^[7]	ND subjects, PD subjects
CKD Stage ^[8]	Stage 3 (30=<eGFR<60), Stage 4 (15=<eGFR<30), Stage 5 (eGFR<15)

NOTES:

- BMI = Body Mass Index
 - See Section 15.6.1 for the subgroup derivations
- [1] Stratum code will be used to determine category. Stratum code=1: ESA non-user, Baseline Hgb <= 9.5, 2: ESA non-user, Baseline Hgb > 9.5, 3: ESA user, Baseline Hgb < 11.0, 4: ESA user, Baseline Hgb >= 11.0.
- [2] Hemocue Hgb at Day 1 will be used for categorization.
- [3] Additional thresholds might be added in order to divide the population equally as appropriate.
- [4] Standardized dose on epoetin i.v. (IU/week) will be used for subgroup.
- [5] Subjects who used ferric citrate (trade name: Riona) will also be included in Baseline Iron Use group. This category will be used just for iron analyses. See Section 15.6.3.
- [6] Past or current history of diabetes
- [7] This subgroup will be used for study population analyses and safety analyses.
- [8] CKD Stage will be determined by eGFR (mL/min/1.73m²) at a screening visit

For prior ESA use, the subgroup of non-users in PD subjects is small. Therefore endpoints summarized for PD subjects (i.e. Safety or Efficacy PD population) by prior ESA use will also be listed for the ESA non-users in PD subjects.

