8. SAFETY ANALYSES

The safety analyses will be based on the Safety population, unless otherwise specified.

The summary will be provided by dialysis (ND and PD separately) and treatment group.

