15.5.3. Reporting Standards for Pharmacokinetic

Pharmacokinetic Concentration Data	
PC Windows Non-Linear (WNL) File	PC WNL file (CSV format) for the non compartmental analysis by Clinical Pharmacology Modelling and Simulation function will be created according to GUI_51487. Note: Concentration values will be imputed as per GUI_51487
Descriptive Summary Statistics, Graphical Displays and Listings	Refer to IDSL PK Display Standards. Refer to IDSL Statistical Principle 6.06.1. Note: Concentration values will be imputed as per GUI_51487 for descriptive summary statistics/analysis and summarized graphical displays only.
Pharmacokinetic Parameter Derivation	
PK Parameter to be Derived by Programmer	The following PK parameters will be derived by the Programmer: 
 Dose Normalized PK parameters
Pharmacokinetic Parameter Data	
Is NQ impacted PK Parameters Rule Being Followed	Yes, refer to [Standards for Handling NQ Impacted PK Parameters].
Descriptive Summary Statistics, Graphical Displays and Listings	Each pharmacokinetic parameter (AUC(0-4), Cmax, and Tmax) will be summarized using the minimum set of summary statistics (IDSL statistical display principle 6.06.1). For each pharmacokinetic parameter (AUC(0-4), Cmax, and Tmax), the log-transformed parameter will be summarized using the summary statistics. The summary statistics are: N, n, geometric mean, 95% CI of geometric mean, standard deviation (SD) of log-transformed data and between subject coefficient of variation (CVb (%)) will be reported. [1] $CV_b (\%) = \sqrt{(\exp(SD^2) - 1) * 100}$ (SD = SD of log transformed data)

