15.6.5. Pharmacokinetic

General
Dose level

 Summaries by dose level and used tablet strength will be based on an actual dose associated with a container number (See Section 15.6.2). Tablet strength is defined as follows: 
 Actual dose = 1 mg → 1 mg tablet strength Actual dose = 2 mg → 2 mg tablet strength Actual dose = 4 mg → 4 mg tablet strength Actual dose = 6 mg → 6 mg tablet strength Actual dose = 8 mg → 4 mg tablet strength Actual dose = 12 mg → 6 mg tablet strength Actual dose = 18 mg → 6 mg tablet strength Actual dose = 24 mg → 6 mg tablet strength Dose level which is actually provided to subjects will be derived from an actual dose of the visit (including unscheduled visit) which meets the following: 
 Treatment Start Date ≤ Date of last dose taken prior to PK sampling ≤ Treatment Stop Date
Others

 Dose normalized PK parameters will be derived from the PK parameters dividing by actual dose (mg). In aggregated analyses, data collected in Week 12 and Week 24 will be aggregated. For the PK parameters calculation, the concentration at 0 hr will be set to 0 and assign zero to NQ values. Individual's PK parameters calculated less than 4-time point concentrations, or any time deviated (beyond ± 30 min of scheduled visits) concentrations, or concentrations obtained in the less interval of last two treatment administrations than 12 hours will be omitted from summaries and figures. but

General
presenting in a listing.

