15.10.4.7. Pharmacokinetic Tables

Pharmacokinetic Tables					
No.	Population	IDSL / TST ID / Example Shell	Title	Programming Notes	SAC
Plasma Daprodustat Concentrations					
5.1.	PK	PK01	Summary of Daprodustat Plasma Concentration by Dose Level (non-transformed)		Y
5.2.	PK	PK_T1 based on PK05	Summary of Daprodustat Plasma Concentration by Dose Level (loge-transformed)		Y
PK parameters					
5.3.	PK	PK03	Summary of Daprodustat Pharmacokinetic Parameters by Dose Level (non-transformed)		Y
5.4.	PK	PK05	Summary of Daprodustat Pharmacokinetic Parameters by Dose Level (loge-transformed)		Y
5.5.	PK	PK03	Summary of Dose Normalized Daprodustat Pharmacokinetic Parameters by Dose level (non-transformed)		Y
5.6.	PK	PK05	Summary of Dose Normalized Daprodustat Pharmacokinetic Parameters by Dose level (loge-transformed)		Y
5.7.	PK	PK03	Summary of Dose Normalized Daprodustat Pharmacokinetic Parameters by Used Tablet Strength (non-transformed)		Y
5.8.	PK	PK05	Summary of Dose Normalized Daprodustat Pharmacokinetic Parameters by Used Tablet Strength (loge-transformed)		Y

CONFIDENTIAL

201753

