15.10.4.8. Pharmacokinetic Figures

Pharmacokinetic Figures					
No.	Population	IDSL / TST ID / Example Shell	Title	Programming Notes	SAC
Plasma Daprodustat Concentrations					
5.1.	PK	PK24	Individual Daprodustat Plasma Concentration-Time Plots	(Linear and Semi-Log) (by Dose)	Y
5.2.	PK	PK17	Mean Daprodustat Plasma Concentration-Time Plots	(Linear and Semi-Log) (by Dose)	Y
5.3.	PK	PK19	Mean (+SD) Daprodustat Plasma Concentration-Time Plots	(Linear and Semi-Log) (by Dose)	Y
5.4.	PK	PK20	Median Daprodustat Plasma Concentration-Time Plots	(Linear and Semi-Log) (by Dose)	Y
PK parameters					
5.5.	PK	PK_F1	Individual Plot of Daprodustat Dose Level and PK Parameters (AUC (0-4) and Cmax)	will provide only pooled data	Y
5.6.	PK	PK_F2	Mean (+SD) Plot of Daprodustat Dose Level and PK Parameters (AUC (0-4) and Cmax)	will provide only pooled data	Y
5.7.	PK	PK_F3	Median Plot of Daprodustat Dose Level and PK Parameters (AUC (0-4) and Cmax)	will provide only pooled data	Y
5.8.	PK	PK_F1	Individual Plot of Daprodustat Dose Level and Dose Normalized PK Parameters (AUC (0-4) and Cmax)	will provide only pooled data	Y
5.9.	PK	PK_F2	Mean (+SD) Plot of Daprodustat Dose Level and Dose Normalized PK Parameters (AUC (0-4) and Cmax)	will provide only pooled data	Y
5.10.	PK	PK_F3	Median Plot of Daprodustat Dose Level and Dose Normalized PK Parameters (AUC (0-4) and Cmax)	will provide only pooled data	Y
5.11.	PK	PK_F4	Box Plot of Daprodustat Dose Level and Dose Normalized PK Parameters (AUC (0-4) and Cmax)	will provide only pooled data	Y
5.12.	PK	PK_F1	Individual Plot of Daprodustat Used Tablet Strength and Dose Normalized PK Parameters (AUC (0-4) and Cmax)	will provide only pooled data	Y
5.13.	PK	PK_F2	Mean (+SD) Plot of Daprodustat Used Tablet Strength and Dose	will provide only pooled data	Y

CONFIDENTIAL

201753

Pharmacokinetic Figures					
No.	Population	IDSL / TST ID / Example Shell	Title	Programming Notes	SAC
			Normalized PK Parameters (AUC (0-4) and Cmax)		
5.14.	PK	PK_F3	Median Plot of Daprodustat Used Tablet Strength and Dose Normalized PK Parameters (AUC (0-4) and Cmax)	will provide only pooled data	Y
5.15.	PK	PK_F4	Box Plot of Daprodustat Used Tablet Strength and Dose Normalized PK Parameters (AUC (0-4) and Cmax)	will provide only pooled data	Y

CONFIDENTIAL

201753

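### The all-visits PK summaries pool Weeks 12 and 24 with no rule for subjects who contribute twice, so their 95% CIs are too narrow

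*SAP*

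**What the plan says.** Section 10.1.2 summarises plasma concentrations and PK parameters at Week 12, at Week 24 and for "all visits (i.e., pooled analysis of Week 12 and Week 24) by dose level". The statistics include the mean or geometric mean with its 95% CI and, on the log scale, a between-subject CV. Dose-normalized parameters are also tabulated by tablet strength. These are Tables 5.1 to 5.8 in 15.10.4.7.

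The only handling rule for the combined set is in 15.6.5: "In aggregated analyses, data collected in Week 12 and Week 24 will be aggregated". The CV formula in 15.5.3 uses a single standard deviation ("SD = SD of log transformed data"). The tablet-strength mapping in 15.6.5 assigns 4 and 8 mg to the 4 mg tablet, and 6, 12, 18 and 24 mg to the 6 mg tablet.

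In 15.10.4.8, Figures 5.5 to 5.15 carry the note "will provide only pooled data".

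On who is included, section 4 defines the PK population thus: "Consists of all GSK1278863-treated subjects from whom PK samples are collected and analyzed". Note [7] of 5.4.2 says of the dialysis subgroup: "This subgroup will be used for study population analyses and safety analyses". Section 8, by contrast, says of safety: "The summary will be provided by dialysis (ND and PD separately) and treatment group".

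**The concern.** Two profiles from one person are usually correlated. If they are stacked and treated as separate observations, the standard error uses the number of records where the information is closer to the number of subjects. The all-visits rows use the most data and so look the most precise; a reader would naturally quote their intervals. Those are the rows whose intervals are wrong.

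Titration does not remove the problem. A subject whose dose changed between visits enters two dose levels once each, which is harmless within each level. In the tablet-strength tables, however, a subject who moved among 6, 12, 18 and 24 mg, or between 4 and 8 mg, still enters one group twice.

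A second and lesser point is that the PK population is not restricted by cohort and no PK table or figure is split by dialysis status. Any ND/PD difference in exposure would be invisible in these displays.

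**Working it through.** The SAP gives no PK sample size, precision target or numeric PK result, so there is no figure to reproduce. What follows is the consequence of the stated rule. The within-subject correlation ρ is an assumption, shown over a range.

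**Confidence interval, every subject contributing twice.** Take n subjects with two log values each, between-subject variance σb², within-subject variance σw², total σ² = σb² + σw², and ρ = σb²/σ².

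- Variance of the mean as computed from the stacked records: about σ²/(2n).
- Actual variance of the mean: σ²(1+ρ)/(2n).
- The correct interval is wider by √(1+ρ), and the SE is understated by 1 − 1/√(1+ρ).
- Large-sample coverage of the stacked interval: 2Φ(1.96/√(1+ρ)) − 1.

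| ρ (assumed) | √(1+ρ) | SE understated by | Coverage |
|---|---|---|---|
| 0.3 | 1.14 | 12% | 91% |
| 0.5 | 1.22 | 18% | 89% |
| 0.8 | 1.34 | 25% | 86% |

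Simulation (20,000 runs, 10, 20 or 40 subjects per cell) agreed: about 91–92%, 89% and 85–86%. One averaged value per subject, with n − 1 degrees of freedom, gave 94.8–95.2% at these correlations.

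**Confidence interval, only some contributing twice.** With n₁ subjects giving one record and n₂ giving two, there are N = n₁ + 2n₂ records, and the variance ratio is 1 + 2n₂ρ/N. If half contribute twice (an illustration), N = 1.5n and the ratio is 1 + 0.667ρ. Coverage is then 2Φ(1.96/√1.20) − 1 = 93% at ρ = 0.3, and 2Φ(1.96/√1.533) − 1 = 89% at ρ = 0.8.

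**Between-subject CV.** The expected squared SD of the stacked set is σb²(2n−2)/(2n−1) + σw². Assume a single-visit CV of 50%, so σ² = ln(1.25) = 0.2231.

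- With n = 10 and ρ = 0.8: 0.1785 × 18/19 + 0.0446 = 0.2137, so CV = √(e^0.2137 − 1) = 48.8%.
- With n = 40 and ρ = 0.8: 49.7%.
- A purely between-subject CV at ρ = 0.3 and 0.8 would be √(e^(ρσ²) − 1) = 26% and 44%.

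Double entry therefore moves the CV by about a point at most here. The gap from a true between-subject CV comes from within-subject variance, which a single-visit CV also contains.

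**ND and PD.** Planned numbers are about 286/2 = 143 ND subjects on daprodustat and about 50 PD subjects, so the expected PD share is 50/193 = 26% if all are sampled. If the PD/ND exposure ratio is r and the PD share is 10% at one dose level and 50% at another (both assumed), the spurious dose-normalized ratio is r^(0.5−0.1) = r^0.4. This is 1.04, 1.09 and 1.18 for r = 1.10, 1.25 and 1.50, and 1.00 if r = 1.

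**The case against.** PK is a descriptive secondary objective. The Week 12 and Week 24 summaries stand beside the pooled rows with no duplication, and the listings give individual data. Doses may change every 4 weeks, so the full double-entry case is a ceiling. The titles of Figures 5.5 to 5.15 call for individual values, means with SD, medians or box plots, not confidence intervals, so the defect is confined to the all-visits rows of the tables. The sponsor's PK display standards and the mock shells are separate documents and might hold a rule not seen here. All of this stands and limits the size of the point. None of it supplies a repeated-records rule in the SAP.

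A reader might go further in two directions that the document does not support.

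- **Exposure and dose proportionality are confounded by dialysis status.** That needs both an ND/PD exposure difference and a PD share that varies by dose. The SAP documents neither, and it plans no dose-proportionality model or test. Sampling of PD subjects is itself inferred from the unrestricted population and from a schedule row with no ND-only mark; the text of that row's footnote is not shown. This is a conditional risk, not a demonstrated bias.
- **The pooled between-subject CV is numerically wrong because of double entry.** The calculation shows that it barely moves. The fault is the label.

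**Conclusion.** The point holds for the 95% CIs in the all-visits rows of Tables 5.1 to 5.8. They are too narrow whenever subjects repeat within a cell and the within-subject correlation is positive. Coverage is about 91% to 86% if all subjects repeat and ρ is 0.3 to 0.8, and closer to 95% as fewer repeat. Both ρ and the proportion repeating are assumptions. The pooled CV needs a different label or separate variance components. The absence of any ND/PD view is a gap in what the displays can reveal and merits a supplement, no more. This is a minor improvement; it does not affect the efficacy conclusions.

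**What to change.** Add to 10.1.2 and 15.6.5: for the all-visits set, reduce each subject to one value within each dose level, and within each tablet strength for the dose-normalized tables by strength. Use the mean of the log-transformed values for log-scale summaries and the mean of the untransformed values for the others, then compute the mean or geometric mean, 95% CI and CV. Alternatively, fit a mixed model with a subject effect, which also allows between- and within-subject CV to be reported separately. For concentrations, average within nominal sampling time.

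As a supplement to the pooled displays, add ND and PD versions, or mark ND and PD with different symbols in the individual dose-normalized plots, and extend note [7] of 5.4.2 to cover PK.

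The cost is one averaging step and one by-variable or plotting symbol in existing programs, with no new data. The drawback is sparse PD cells: about 50 subjects over eight non-zero dose levels is roughly 50/8 ≈ 6 per level at a visit, fewer after the PK exclusions. Individual values may be more useful there than summary statistics.
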